RELAIS : RCT on Evaluation of Late Iugr Screening

Single scan screening of fetal growth restriction versus Longitudinal Scan screening in the third trimester: a multicenter randomized protocol

NCT05787054

Date of Approval 19th February 2019

Background	2
AIM	3
STUDY DESIGN	4
Type of study:	4
Inclusion criteria:	4
Exclusion criteria:	4
Study protocol:	4
Measurements of outcome	5
MAIN OUTCOME	6
SECONDARY OUTCOME	6
TERTIARY OUTCOME	6
EXPECTED RESULTS	6
STATISTICS	6

Background

In Italy, the universal sonographic pregnancy screening based on three examinations with the introduction of a third scan at 28-32 weeks of gestation failed its original aim to screen IUGR fetuses. Except for the very few early severe cases of IUGR that occur before 28 weeks of gestation (approximately 0.2%), the vast majority of fetal growth disorders occur later in gestation and are frequently missed by the early third trimester scan at 28-32 weeks of gestation.

As a result of clinical uncertainties many ultrasound examinations are then performed on the ground of "clinical indication" (M50 prescriptions). According to the CeDAP report for the year 2014, 41% of all pregnancies undergo four to six obstetrical sonographic examinations and 32% more than seven!

An even worse, unwanted result, of the Italian protocol is that "normal" scans at 30 weeks of gestation falsely reassure the clinician that might underestimate fetal growth restriction in late preterm or term pregnancies, with unexpected poor obstetrical outcomes in Labor and Delivery.

This failure puts the ground of the idea of uselessness of this early third trimester sonographic fetal growth checkpoint and the need of its cancellation.

In the meantime new scientific evidence showed the possible positive effects on neonatal outcome of a different protocol based on late third trimester screening.

Recent studies from UK, Sweden, Spain and France all agree that ultrasound on indication in the third trimester or screening in the early third trimester do not achieve any better sensitivity than 20% in detecting SGA, whereas late third trimester universal screening reaches and goes beyond 60% of SGA, especially when associated with uterine Doppler velocimetry.

Late and term IUGR fetuses, undergo major cardiovascular adaptation to cope with restricted nutritional supply from the placenta. These concepts emerged from evidences in experimental trials on animals, in the last decades were proved in severe IUGR human fetuses, and in the last five years had been confirmed in late and term IUGR, by means of Doppler investigation of fetal circulation and unquestionable evidence from flow volume studies in human fetuses by functional NMR. These studies all provide a solid ground for the epidemiological evidence put forward by JA Barker on the "fetal origin of coronary heart disease", a truly scientific breakthrough that opened the whole new era of "fetal programming".

This solid scientific background tells us clinicians that undetected problems of fetal growth restriction not only are an unfortunate condition for perinatal complication that should be tackled by wise and efficient clinical protocols with the aim to reduce immediate health threats to our newborns but also to flag these cases so that paediatricians and family doctors could threeimplement healthy lifestyles to prevent the forecasted metabolic and cardiovascular complication pending on these subjects.

In fact, this new focus on fetal growth is paralleled by a quest for a more dedicated attention to growth disorders in utero that, via altered fetal programming, might cause long term metabolic and cardiovascular problems. We quote this editorial published by The Lancet by the intramural director of the NIHCD, dr Roberto Romero: *"A general principle in developmental biology is that organisms are most susceptible to insults during periods of rapid growth. Therefore, it is somewhat paradoxical that even though the human growth rate is particularly rapid during fetal life, monitoring such growth in women with low-risk pregnancies is not part of standard obstetrical care. This situation persists despite overwhelming evidence that fetal growth disorders are risk factors for adverse perinatal outcome and can predispose these infants to adult chronic diseases."*

These data lay down a possible revision of guidelines such as the NICE guideline on Antenatal Care published in 2008 and confirmed in January 2017 under the heading of "1.10 Fetal growth and well-being":

- 1.10.2 Ultrasound estimation of fetal size for suspected large-for-gestational-age unborn babies should not be undertaken in a low-risk population. [2008]
- 1.10.3 Routine Doppler ultrasound should not be used in low-risk pregnancies. [2008]
- 1.10.9 The evidence does not support the routine use of ultrasound scanning after 24 weeks of gestation and therefore it should not be offered.

The sum of biological and clinical evidence with the observation that more than 70% of pregnant women in Italy undergo more than 4 scans per pregnancy, and that even in well-organized regions such as Lombardy and Emilia Romagna more than 25% undergo more than 6 scans per pregnancy, makes a national based study mandatory on efficacy and efficiency of ultrasound screening of fetal growth restriction in order to comply with the criteria that international guidelines should be “tailored” according to local characteristics, clinical organization, cultural values, and, when possible, to local scientific evidence.

AIM

Given the evidence that the universal sonographic screening is far much better than selective screening in detecting fetal growth disorders (1), the aim of this trial is to assess the efficacy and efficiency of two universal sonographic screening protocols for fetal growth disorders:

- the “single scan” **screening** according to the local LEA, based on evaluation of fetal biometry at 28-32 weeks of gestation (in the Regions where the “early screening” is recommended) as it is in the Italian NHS protocol, after ultrasound dating at 10-13 weeks of gestation and anatomy screening and fetal biometry at 19-22 weeks of gestation.
- the **longitudinal screening**, similarly providing a scan at 10-13 weeks of gestation for dating, and a second scan at 19-22 weeks of gestation based on biometric and Uterine artery Doppler velocimetry procedure, and subsequently both one scan at 28-32 weeks and another one at 35-37 weeks of gestation.

STUDY DESIGN

Type of study:

multicentre diagnostic, open randomised trial.

Inclusion criteria:

Eligible cases are **nulliparous pregnant women**, with first trimester ultrasound assessment of gestational age, **who conceived singleton fetuses**. If the crown-rump-length (CRL) differs of more than $\pm 3-5$ days from the last menstrual period, gestational age is calculated on the CRL. Women who agree to participate are randomized to the Single scan protocol or Longitudinal scan protocol. In practical terms this means that in each participating centre the randomization will be on two arms but the time of the single scan assessment will be dependent on the Regional Health Authority regulation (LEA: Livelli Essenziali di Assistenza)

Exclusion criteria:

- major medical disease
- pregnancy conceived by IVF/ICSI
- known immune disorders or clinical thrombophilic conditions;
- twin pregnancies;
- high risk for preeclampsia detected in those centres that perform pre-eclampsia screening at first trimester
- Papp-A at Combined-Test<0.2

Study protocol:

Eligibility check, information on this trial, offer to be recruited will be performed by the local investigator at the 19-21 weeks of gestation scan.

Women who agree to take part into the trial and sign an informed consent, will be randomized **to the Single Scan Protocol (28-32 weeks scan) or to the Longitudinal Scan Protocol (scan both at 28-32 AND 35-37 weeks)**. Demographic characteristics and medical history of recruited women are recorded on the CRF. The same demographic and clinical data of eligible women who refuses to be recruited will be recorded for analysis between trial cohort and eligible non recruited women. To define fetal growth disorders we will adopt the Delphi criteria for the diagnosis of IUGR.

Women randomized to the **Single scan Protocol** will receive the standard package of sonographic anatomy and biometric screening offered by the Regional Health Service at 19-21 weeks of gestation and biometric screening at 28-32.

- **Single Scan protocol at 19-21 weeks:** if **AC biometry and/or fetal weight are normal** a biometric scan is scheduled basing on the regional LEA at 28-32 weeks of gestation .If **AC biometry and/or fetal weight are abnormal the case is excluded** from further analysis for third trimester screening, and the patient is then monitored according to local protocol.
- **Single Scan at 28-32 weeks:** if **AC biometry and/or fetal weight is abnormal <10th, or crossed 50th centile from mid-trimester (screen positive)** further management will be performed according to local protocols.

All suspected fetal anomalies will be excluded from further analysis.

Women randomized to the **Longitudinal Scan Protocol**, besides the fetal anatomy screening, will receive a package of anatomy and biometric screening and Doppler interrogation of the Uterine arteries at 19-21 weeks of gestation and at 28-32 and 35-37 according to the following criteria:

- **Longitudinal Scan Protocol at 19-21 weeks:** if both **AC biometry and/or fetal weight** a biometric scan is scheduled at 28-32 weeks of gestation regardless the result of the Uterine Artery Doppler investigation. If **AC biometry and/or fetal weight are abnormal the case is excluded** from further analysis for third trimester screening, and the patient is then monitored according to local protocol
- **Longitudinal Scan Protocol at 28-32 weeks:** a standard package of fetal biometry, Amniotic Fluid index and Doppler interrogation of the Uterine arteries, Umbilical artery and Middle cerebral artery will be performed. If the **AC biometry and/or fetal weight** are normal, another biometric scan will be scheduled at 35-37 weeks of gestation and monitored until delivery according to local protocols (**screen negative**).
- **Longitudinal Scan Protocol at 35-37 weeks:** a standard package of fetal biometry, Amniotic Fluid index and Doppler interrogation of the Uterine arteries, Umbilical artery and Middle cerebral artery will be performed. If **AC biometry and/or fetal weight is abnormal <10th, or crossed 50th centile from mid-trimester (screen positive)** further management will be performed according to local protocols.

All scans after the dating scan in the first trimester are performed with mid-high quality ultrasound units. All ultrasound measurements follow the same protocols as those used in the clinical service, i.e. measurement of fetal head circumference, abdominal circumference, and femur length, using standard techniques.

Images produced to obtain recorded measurements are stored on digital media.

Attending clinicians are informed of the results obtained both by the Single Scan and by the Longitudinal Scan Protocols and will act according to local protocols when a diagnosis of IUGR is the result of the scan.

Measurements of outcome

This study is designed to generate level 1 evidence of diagnostic effectiveness

For both protocols, screen positive and screen negative results are based on the antenatal detection of a small for gestational age (SGA) neonate namely a newborn with a birth weight $<10^{\text{th}}$ centile.

MAIN OUTCOME

The main outcome of the two protocols in screening late preterm and term SGA fetuses at term is measured based Intergrowth21th newborn weight charts centiles $<\text{the } 10^{\text{th}}$ according to gender.

SECONDARY OUTCOME

1. Mode of delivery
2. Caesarean section rate
3. Composite mild adverse neonatal outcome (Apgar score at 5 minutes <7 , pH < 7.10 , or BD $>8\text{mmol/L}$, admission at NICU)
4. Composite severe adverse perinatal (stillbirth or term live birth associated with neonatal death, hypoxic ischaemic encephalopathy, use of inotropes, need for mechanical ventilation, or severe metabolic acidosis (defined as a cord blood pH <7.0 and base deficit $>12 \text{ mmol/L}$).

TERTIARY OUTCOME

1. Econometrics of the two protocols, and of the estimated sanitary costs of outcomes

EXPECTED RESULTS

We hypothesize that the Longitudinal Scan Protocol with a 28-32 AND a 35-37 weeks universal screening will outperform the Single scan Protocol for the primary outcome regarding the detection Rate of IUGR. On the other hand, as this Protocol will be the more expensive one, we hypothesize that the most cost effective protocol will be the universal single late scan at 35-37 weeks of gestation so underlying the clinical utility of a late single scan for the low risk population.

The secondary outcomes are subjected to local protocols and we should expect a reduction of the composite neonatal adverse outcome in the late single scan protocol and in the longitudinal one. Last but not least, we hypothesize that the inferred Econometrics of the two protocols will provide evidence of the reduced health care costs of the universal screening when properly based on biological and clinical data obtained by this branch of medicine in recent years (R.P.) versus old tenets of the early years of the introduction of ultrasound in obstetrics (I.P.).

STATISTICS

Sample size is based on sensitivity in detecting SGA below 10th centile weight at birth. For the 28-32 group, sensitivity is based on results by Roma et al. (22.5%). The results published by Sovio et al. are instead taken for the “longitudinal” group (57% sensitivity).

The sample size calculations have been carried out for the comparison between the 28-32 only group vs. the “longitudinal”. Calculations considered a confidence level of 95% (1-alpha) and an 80% power (1-beta), and a one to one ratio between the 28-32 only groups and the “longitudinal”. According to Fleiss (Fleiss JL. Statistical methods for rates and proportions, II Ed. John Wiley & Sons, New York, 1981. page 45, formulas 3.18 & 3.19), for the 28-32 group vs. the “longitudinal”, each arm should comprise 32 subjects, which implies 64 for two arms. The sample size needed considering both AGA and SGA, will then be $64 \times 10 = 640$. Considering 10% of drop-out and incomplete data the final sample size should be increased of such percentage, reaching 704 subjects.

The sample should be recruited according to the number of deliveries per year of each institute involved in the multicenter study. Analysis will be based on intention to treat. Demographic and maternal characteristics variables will be collected in order to describe the population of women recruited in the study and reassure about the result of randomization

A Kolmogorov-Smirnov or Shapiro-Wilk test and visual plot inspection will be used to assess normality of arithmetic data distributions. Parametric or non-parametric tests will be used to compare variables between the groups, and comparison of proportions will be performed using Chi-square or Fisher’s exact test, as appropriate.

Logistic regression models will be used to determine the magnitude of the association between ultrasound variables and newborn’s weight $<10^{\circ}$ centile and neonatal outcome.

Performance of Single Scan and Longitudinal Scan screening policy in identifying late preterm and term SGA will be calculated and compared between arms. The area under the receiver operating characteristic (ROC) curve will be estimated with 95% confidence intervals. Next, the screening performance will be then summarized in terms of sensitivity, specificity, positive and negative predictive values and likelihood ratios.

A p value <0.05 will be considered statistically significant.

Figure 1 : Flow chart of the randomized trial

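### Whole-cohort secondary outcomes are to be compared without a centre term, although women are randomised in each centre and these outcomes depend on local practice; the cost is precision, not false positives

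*Combined protocol and SAP*

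**What the plan says.** **Allocation.** Under STUDY DESIGN, Inclusion criteria, women are randomised individually: "in each participating centre the randomization will be on two arms but the time of the single scan assessment will be dependent"; what governs the timing is regional regulation. The protocol does not say whether allocation is stratified or blocked by centre.

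**Local influence.** Under Study protocol, after a positive screen "further management will be performed according to local protocols", in both arms. EXPECTED RESULTS adds: "The secondary outcomes are subjected to local protocols". The binary secondary outcomes are caesarean section and the mild and severe composites.

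**Analysis.** In STATISTICS, "comparison of proportions will be performed using Chi-square or Fisher" (the exact test being the alternative to chi-square). For other data, "Parametric or non-parametric tests will be used to compare variables between the groups". Screening performance, including ROC area, is compared between arms with no test named. The regression is a separate item: "Logistic regression models will be used to determine the magnitude of the association between ultrasound variables and" birth weight and neonatal outcome, so it is not described as an arm comparison. Centres appear in this section only where recruitment is set by deliveries per year. The numbers of centres and regions are not given.

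**The concern.** The protocol itself names local practice as a determinant of the secondary outcomes, and centres that differ in, say, caesarean rate will contribute women to both arms. A pooled 2x2 test leaves that between-centre variation in its error term. A stratified test removes it at almost no cost when every analysed woman contributes, because the strata are then not sparse. At stake is whether the trial can detect a real difference in these outcomes, and whether the reported interval is wider than it needs to be. The validity of a positive result is not at stake.

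**Working it through.** **1. The plan's own figure.** Inputs from EXPECTED RESULTS and STATISTICS: sensitivity 22.5% versus 57%, 80% power, 95% confidence, 1:1. The two-sided formula without continuity correction is

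n = [1.96√(2p̄q̄) + 0.842√(p₁q₁ + p₂q₂)]² / (p₂ − p₁)²

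With p̄ = 0.3975: (1.356 + 0.545)² / 0.345² = 3.616 / 0.1190 = 30.4, so 31 per arm against the stated 32. Power at 32 per arm is 82.1%. Then 64 × 10 = 640 women, and 640 × 1.10 = 704. The figure reproduces to within one woman per arm, and the present point does not alter it.

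**2. Whole-cohort outcomes: assumptions.** The documents give no event rates, number of centres or between-centre variation. I assume 640 women, 8 or 16 equal centres, 25% versus 35% in a typical centre, and normal centre effects on the log-odds shared by both arms, with SD 0, 0.5 or 1.0. Around 25%, one SD either way spans 17% to 35% at SD 0.5 and 11% to 48% at SD 1.0, so the larger value is strong variation.

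**3. Why the pooled test becomes conservative.** With allocation balanced by centre, the true null variance of the arm difference is proportional to the mean of p_k(1 − p_k) over centres. The pooled test uses p̄(1 − p̄). The ratio of the two is 1 − Var(p_k)/[p̄(1 − p̄)].

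- SD 0.5: mean 0.261, variance 0.0087. Ratio = 1 − 0.0087/0.193 = 0.955. Type I error = 2Φ(−1.96/√0.955) = 4.5%.
- SD 1.0: mean 0.286, variance 0.0316. Ratio = 1 − 0.0316/0.204 = 0.845. Type I error = 2Φ(−1.96/√0.845) = 3.3%.

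Simulation (20,000 trials per setting) agrees: about 4.5% at SD 0.5 and 3.0-3.9% at SD 1.0 for the pooled test, against about 5% for CMH. With simple, unbalanced randomisation the pooled test stays near 5%.

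**4. Power.** The CMH statistic is [Σ(x₁ₖ − n₁ₖtₖ/nₖ)]² / Σ[n₁ₖn₀ₖtₖ(nₖ − tₖ)/(nₖ²(nₖ − 1))]. In centre k, x₁ₖ is the number of events in one arm, n₁ₖ and n₀ₖ are the arm sizes, tₖ is the total events and nₖ the total women.

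| Between-centre SD | Pooled chi-square | CMH by centre |
|---|---|---|
| 0 | about 79% | 77-79% |
| 0.5 | 75-77% | 76-78% |
| 1.0 | 66-68% | 72-73% |

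A repeat run agreed within about 1 point. Part of the fall down the table arises because a fixed odds ratio gives a smaller average difference when centres vary. If the overall rates are held at 25% and 35% instead, with balanced allocation, the pairs are 79% versus 79%, 80% versus 81% and 81% versus 85%. The gain at SD 1.0 is about 4 to 6 points on either scale.

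**5. The primary endpoint.** It uses only the roughly 64 SGA births (22.5% versus 57%). Pooled versus CMH power, with a centre or region effect shared by both arms:

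- No heterogeneity: about 82% versus 79% with 4 strata, 81% versus 77% with 6, and 82% versus 70% with 16 centres.
- SD 0.5: 82% versus 81% with 4 strata, 82% versus 80% with 6.
- SD 1.0 with 4 strata: 83% versus 85%.

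If region alters only the Single-scan arm, CMH does not gain: with 4 strata it is 79.7% versus 77.9% (SD 0.5), 77.4% versus 76.3% (SD 1.0) and 75.5% versus 74.8% (SD 1.5). The pooled type I error for this endpoint is 4.8-5.4% throughout.

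**The case against.** The strongest reply is that nothing here is invalid. The pooled test does not exceed its nominal level, the gain is small unless centres differ a good deal, and the conservatism needs balanced allocation, which the protocol does not state. All of that stands, and it limits the point to precision.

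A reader might go further in three ways that the documents do not support.

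- **That the primary comparison should be stratified by regional Single-scan timing.** AIM and Study protocol both place the Single scan at 28-32 weeks, and the trial is sized on that group, so timing strata are not defined and there may be only one. With about 64 SGA births, four strata leave about 8 per arm in each (64/8), too few to show whether the arm contrast varies. A gain appears only if a large regional effect is shared by both arms, and timing of the Single scan would act on one.
- **That every arm comparison is an unstratified chi-square or Fisher test.** Those tests are named for proportions only; other variables get other tests, and none is named for ROC area and performance. The absence of stratification is read from silence.
- **That allocation was stratified by centre, so the analysis must follow it.** The text says that both arms exist in each centre, not how the list was built.

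None of these replies removes the case for whole-cohort outcomes, where stratifying costs at most about 1 point.

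**Conclusion.** The point holds for the binary secondary outcomes to which all analysed women contribute. Omitting centre costs about 4 to 6 points of power at a between-centre SD of 1.0 and about 1 point at SD 0.5. It gains at most about 1 point when centres do not differ. If allocation is balanced by centre, the pooled test runs at about 3-4% instead of 5% at SD 1.0. These sizes rest on assumed rates, centre numbers and SDs; the gain could be smaller for a rare outcome such as the severe composite may be. There is no false-positive risk and no effect on the sample size. The primary comparison of sensitivity is better left unstratified.

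**What to change.** In STATISTICS:

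1. State how women are allocated, including whether the list is stratified or blocked by centre.
2. Compare caesarean section and the two composites with a CMH test and a Mantel-Haenszel risk difference (95% CI) stratified by centre, pooling very small centres by region under a rule fixed in advance. Report the unstratified test as a sensitivity analysis.
3. Keep the unstratified comparison of sensitivity as primary. A region-stratified or random-centre version may be reported as a sensitivity analysis only.
4. Reconcile the passages on Single-scan timing. Inclusion criteria make it depend on the regional authority, and Study protocol says "a biometric scan is scheduled basing on the regional LEA at 28-32 weeks of gestation". EXPECTED RESULTS, however, anticipates results for a late single-scan protocol that the two-arm design does not contain.

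The cost is wording in the plan, plus up to about 1 point of power on the secondary outcomes if centres turn out not to differ. No extra women are needed, and the centre is known for every woman.

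### The clauses for a normal scan misuse and/or: at 19-21 weeks a fetus with one abnormal measure is both kept and excluded, and at 28-32 weeks one low measure is screen positive in one arm and literally screen negative in the other.

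*Combined protocol and SAP*

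**What the plan says.** All the rules stand under STUDY DESIGN, Study protocol.

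- **19-21 weeks, Single Scan arm.** If "AC biometry and/or fetal weight are normal", the woman goes on to the 28-32 week scan. The next sentence says that if "AC biometry and/or fetal weight are abnormal the case is excluded" from the third-trimester analysis.
- **19-21 weeks, Longitudinal arm.** The exclusion clause is the same. The continue clause puts the word both in front of the and/or phrase, never says what the measures must be, and then states that "a biometric scan is scheduled at 28-32 weeks of gestation regardless the result of the Uterine Artery Doppler investigation".
- **28-32 weeks, Single Scan arm.** Screen positive if "AC biometry and/or fetal weight is abnormal <10th, or crossed 50th centile from mid-trimester (screen positive"). No normal clause is written.
- **28-32 weeks, Longitudinal arm.** If AC and/or fetal weight "are normal, another biometric scan will be scheduled at 35-37 weeks of gestation and monitored until delivery according to local protocols"; this is labelled screen negative. No positive clause is written.
- **35-37 weeks, Longitudinal arm.** The positive clause has the same wording as in the Single Scan arm at 28-32 weeks. No normal clause is written.

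The same section also states: "To define fetal growth disorders we will adopt the Delphi criteria for the diagnosis of IUGR". It does not link those criteria to the screen result. Under MAIN OUTCOME, the reference standard is birth weight: "The main outcome of the two protocols in screening late preterm and term SGA fetuses at term is measured based Intergrowth21th newborn weight charts centiles" below the 10th. Under STATISTICS: "Sample size is based on sensitivity in detecting SGA below 10th centile weight at birth".

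**The concern.** And/or does different work in an abnormal clause and in a normal clause. To call a scan abnormal if either measure is abnormal is a clear rule. Its complement is that both measures are normal. If the normal clause also says and/or, one normal measure satisfies it, and the two clauses overlap for every fetus whose measures disagree.

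Two things are at stake. The first is who is analysed: the 19-21 week exclusion is written into each arm's schedule, and for a fetus with discordant measures it contradicts the clause beside it. The second is the screen result itself. Screen status enters sensitivity, specificity, the predictive values and the likelihood ratios that STATISTICS compares between arms. If one finding at one gestation counts as positive in one arm and negative in the other, part of any difference in sensitivity comes from the wording and not from the extra scan. The trial is open, so the arm is known when a discordant case is labelled.

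**Working it through.** **Step 1: the planned figure.** STATISTICS gives sensitivities of 22.5% and 57%, 95% confidence, 80% power, 1:1 allocation and 32 SGA cases per arm. With p1 = 0.225, p2 = 0.57 and mean 0.3975, two-sided and without continuity correction:

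n = [1.960 × √(2 × 0.3975 × 0.6025) + 0.842 × √(0.225 × 0.775 + 0.57 × 0.43)]² / 0.345² = 30.4, rounded up to 31.

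That is within one of the stated 32 (with continuity correction it is 36). Power at 32 per arm is 82.1%. Then 64 × 10 = 640 and 640 × 1.10 = 704, as stated. This confirms that the comparison rests on sensitivity in about 32 SGA cases per arm.

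**Step 2: one discordant fetus, taken through each visit literally.** One of AC and estimated weight is abnormal (below the 10th centile at the third-trimester scans) and the other is normal; the centile-crossing limb is not met.

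| Visit | Single Scan arm | Longitudinal arm |
|---|---|---|
| 19-21 weeks | Meets continue and exclude | Meets exclude; the continue clause has no predicate |
| 28-32 weeks | Screen positive | Meets the screen-negative clause; no positive clause exists |
| 35-37 weeks | No scan | Screen positive |

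The contradiction within a visit is at 19-21 weeks in the Single Scan arm. The contradiction between arms is at 28-32 weeks. If the Longitudinal 19-21 week sentence was meant to require both measures normal, the two arms also have different continue clauses.

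**Step 3: how many fetuses could be affected at one scan.** The documents give no correlation between AC and estimated weight. Assume that their z-scores are bivariate normal with correlation r between 0.8 and 0.9, and that each is below the 10th centile in 10% of fetuses (z = −1.2816). Exactly one below = 20% − 2 × P(both below).

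| r | Both <10th | At least one <10th | Exactly one <10th |
|---|---|---|---|
| 0.80 | 5.6% | 14.4% | 8.8% |
| 0.85 | 6.2% | 13.8% | 7.6% |
| 0.90 | 6.9% | 13.1% | 6.2% |

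In the 320 women per arm before the dropout allowance (640 / 2), that is about 20 (0.062 × 320) to 28 (0.088 × 320) women at one scan. The figure ignores the centile-crossing limb, which would make some of them positive anyway. It applies at 19-21 weeks only if the 10th centile is the cut-off there, and no cut-off is written for that visit.

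**Step 4: what an arm-specific rule could do to power.** This is an illustration only, because the share of SGA fetuses with discordant measures is not in the documents. Suppose that share is counted negative and lowers sensitivity by the same amount.

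| Assumed share | Longitudinal arm only: sensitivity | Power at 32 per arm | Both arms: power at 32 per arm |
|---|---|---|---|
| 0% | 57% | 82% | 82% |
| 5% | 52% | 69% | 84% |
| 10% | 47% | 54% | 87% |
| 15% | 42% | 38% | 91% |

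The middle columns hold the Single Scan arm at 22.5%. A reading shared by both arms does not cost power in this illustration; a difference between arms does.

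**The case against.** The strongest reply is that the rules that declare a woman positive are clear. A reader might infer that a fetus with one low measure has no single value of the primary endpoint anywhere in the trial. The documents do not support that. At 28-32 weeks in the Single Scan arm and at 35-37 weeks in the Longitudinal arm only a positive clause is written, so either measure below the 10th centile makes the scan positive. The reference standard, birth weight, is not touched either.

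It can also be said that the 19-21 week overlap decides continuation and not screen status, and that a discordant Longitudinal fetus at 28-32 weeks is scanned again at 35-37 weeks under the clear rule. Both are true. The first narrows the harm to the analysed set. The second means that the effect of the 28-32 week label depends on how the two Longitudinal scans combine into one result, which the plan does not say. Neither removes the conflict in the text.

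A second tempting step is to model an either-measure rule against a both-measures rule and set the gap in one scan's sensitivity against the planned difference of 34.5 points (57 − 22.5). That is not like for like. It concerns one scan, not a contrast between arms. It needs further assumed correlations with birth weight, and it omits the centile-crossing limb. Randomisation takes place within each centre, so a site's reading of the identically worded positive rule would apply to both arms. Nor can it be said that the 22.5% and 57% do not match the test used here, since the documents do not give the test definitions behind those values.

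**Conclusion.** The point holds in a limited form. Read literally, the plan (a) both keeps and excludes a Single Scan fetus with one abnormal measure at 19-21 weeks, and the defective Longitudinal sentence does not settle the matter; and (b) gives the same 28-32 week finding opposite labels in the two arms, inside a comparison of sensitivity. Neither the Delphi criteria nor the birth-weight definition resolves this.

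The group concerned is about 6-9% of fetuses at one scan, on the assumption of bivariate normality and a correlation of 0.8-0.9 between AC and weight. The effect on the difference between arms cannot be computed from the documents. It depends on the share of SGA fetuses with discordant measures, on how the two Longitudinal scans are combined, and on how sites read the clauses. The power figures show only that an arm-specific rule is the harmful kind. The plan should be corrected, because the text as it stands cannot be followed without contradiction and the repair is cheap.

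**What to change.** For the endpoint only, derive screen status centrally, with the same rule in both arms at each third-trimester scan, following the protocol's own positive clause:

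- positive if at least one of AC or estimated weight is below the 10th centile, or the centile-crossing limb is met;
- negative only if none of these is met.

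Report as a sensitivity analysis the version in which both measures must be below the 10th centile. State alongside it how the two Longitudinal scans form one result, because the derived variable needs that.

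The continue and exclude clauses at 19-21 weeks, in both arms, and the Longitudinal 28-32 week clause must be reconciled so that no woman meets two opposing clauses. Which clinical rule to adopt is for the investigators and is not judged here.

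The cost is a short protocol clarification and one derived variable, with no extra women or scans. Derived status may differ from the site's label in a few women. Centiles may have to be computed from the recorded measurements on one named chart, since the protocol names no fetal size chart.
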